5.3 Secondary Analysis

If the null hypothesis for the primary analysis is rejected with a one-sided 5% significance level, an additional secondary analysis will be performed testing superiority, where the superiority margin is $-\delta$. The null hypothesis for the secondary analysis is that the difference between the mean change in crestal bone levels for the treatment and control groups is at most the superiority margin (indicating non-superior bone gain). Rejection of the null hypothesis indicates the observed data supports the alternative hypothesis that the difference between the mean change in crestal bone levels for the treatment and control groups is greater than the superiority margin (indicating superior bone gain). The hypotheses associated with the secondary analysis are defined as:

- $H_0: \mu_c - \mu_s \leq -\delta$
- $H_1: \mu_c - \mu_s > -\delta$

where μ_c , μ_s , and δ are defined as above. The hypotheses will be tested using a one-sided t-test with a 5% significance level.

6 Analysis of Secondary Effectiveness Endpoints

All secondary effectiveness endpoints will be summarized descriptively without hypothesis testing.

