7.3.4 ADE Reporting

Adverse device effects must be recorded and submitted to Straumann by completing the AE case report form in the EDC system within five working days of awareness of the event. Safety reporting to the Institutional Review Board (IRB) should occur according to the requirements of the local IRB.

Bone loss reporting: Continuous substantial reduction of the peri-implant bone level is a sign of failure of the implant system. The first European Workshop on Periodontology specified an average marginal bone loss of less than 1.5 mm bone loss within the first year after the insertion of the prosthesis, and thereafter less than 0.2 mm annual bone loss as criteria for measuring success¹⁸. This has been a standard and a basis for success criteria since it was defined in 1993. In a more recent meta-analysis, the authors looked at Straumann implants and determined that a pooled weighted mean of marginal bone level change for Straumann implants was -0.56 mm (95% CI -0.661, -.481) after 5 years. The individual study means of marginal bone level change ranged from -0.15 to -1.0 mm after 5 years.¹⁹ Based on this information the central radiologist will flag any bone level changes that are greater than 2.5 mm in the first year post-loading and any annual changes greater than 1.5 mm in subsequent years. The study manager will review the flagged values and discuss with the principal investigator whether the bone level change will be reported as an ADE.

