8.1 Sample Size

The following assumptions were used to determine the sample size for the primary endpoint of mean change in crestal bone level between implant placement and 12 months postimplant loading:

- Subjects will be assigned to either the test or control treatment group
- The primary analysis is a non-inferiority comparison of the test treatment to the control treatment

- The standard deviation for both test and control treatments is 0.5 mm
- A difference between treatment groups of ≥ 0.5 mm is considered clinically significant (i.e., the non-inferiority margin)
- The difference between the treatment groups is expected to be 0 mm
- Greater than 80% power is considered sufficient
- Statistical test will be performed with a one-sided 5% significance level

The hypotheses associated with the primary endpoint are defined as follows:

$$H_0$$
: $\mu_c \ge \mu_s + \delta$

$$H_1$$
: $\mu_c < \mu_s + \delta$

where μ_c is the mean change in crestal bone level for the test implants, μ_s is the mean change in crestal bone level for control implants, and δ is the pre-defined non-inferiority margin of 0.5 mm. The study will be considered successful if the null hypothesis is rejected, i.e., the conclusion of non-inferiority is achieved. If non-inferiority is achieved at a one-sided α of 5%, a one-side superiority test will be performed at significance level of 5%.

To maintain at least 80% power to detect a difference between treatment groups of 0.5 mm with a common standard deviation of 0.5 mm, 14 subjects per treatment group would be required for a total of 28 subjects. Adjusting for potential 25% attrition, 19 subjects per treatment group will be required for a total of 38 subjects. An additional 14 subjects will be enrolled in order to provide more data for the implant success and survival calculations, thereby bringing the total sample size to 52.

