10.3.1	Pooling Across Centers	10
10.3.2	Pooling Across Protocol Versions at Enrollment	10
10.4	HANDLING OF MISSING DATA.....	11
10.5	OTHER DATA SUMMARIES.....	11
10.6	CHANGES TO PLANNED ANALYSES	11
10.7	STATISTICAL SOFTWARE	11

1 Purpose of the Statistical Analysis Plan

The purpose of this Statistical Analysis Plan (SAP) is to summarize the statistical methodologies being used to confirm the primary effectiveness endpoint and assess the secondary effectiveness, additional effectiveness, and safety endpoints of the immediate implantation of the Straumann® Bone Level Tapered Implant (study device). The SAP will be used should there be any discrepancies with the protocol.

2 Study Design

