4.4 Safety Endpoints

The safety endpoints are defined as the number of adverse events or adverse device effects experienced and the number and proportion of subjects experiencing an adverse event or adverse device effect throughout the study.

5 Analysis of Primary Effectiveness Endpoint

The primary effectiveness endpoint evaluates the difference in the change in mean crestal bone levels from implant loading to 12 months post-implant loading between the treatment and control groups. The change is defined as the mean crestal bone level of the mesial and distal aspects of the implant at 12

months post-implant loading minus at implant loading and the difference is defined as the change for the treatment group minus the control group.

The mean crestal bone levels at each visit, and the change in mean crestal bone levels will be summarized for each group with the count, average, standard deviation, median, minimum, and maximum. The mean change in crestal bone levels will also be categorized as Gain (>0), No change (0), Loss <1 mm, Loss <2 mm, Loss <3 mm, or loss ≥ 3 mm and summarized with the number and proportion of subjects in each category for each treatment group.

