5.2 Primary Analysis

The null hypothesis for the primary analysis is that the difference between the mean change in crestal bone levels for the treatment and control groups is at least the non-inferiority margin (indicating inferior bone gain). Rejection of the null hypothesis indicates the observed data supports the alternative hypothesis that the difference between the mean change in crestal bone levels for the treatment and control groups is less than the non-inferiority margin (indicating non-inferior bone gain). The hypotheses associated with the primary analysis are defined as:

- $H_0: \mu_c - \mu_s \geq \delta$
- $H_1: \mu_c - \mu_s < \delta$

where μ_c is the mean change in crestal bone levels from implant loading to 12 months post-implant loading for the treatment group, μ_s is the mean change for the control group, and δ is the 0.5 mm non-inferiority margin. The hypotheses will be tested using a one-sided t-test with a 5% significance level.

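### SAP 5.3 calls it superiority when the test arm is shown to be less than 0.5 mm worse than control; identical arms would be called superior in about 91% of trials (SD 0.5 mm, 23 per arm)

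*SAP*

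**What the plan says.** The opening of SAP section 5 fixes the signs. Change is the 12-month level minus the level at loading, and "the difference is defined as the change for the treatment group minus the control group". The change "will also be categorized as Gain (>0), No change (0"), followed by the loss categories, so larger values are better. SAP 5.2 makes μc the treatment group, μs the control group and δ 0.5 mm.

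SAP 5.3 applies only if the 5.2 null is rejected; in that case "an additional secondary analysis will be performed testing superiority, where the superiority margin is" −δ. It tests H0: μc − μs ≤ −δ against H1: μc − μs > −δ at one-sided 5%. The alternative is also put in words: the difference between treatment and "control groups is greater than the superiority margin (indicating superior bone gain").

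The gate in 5.2 has H1: μc − μs < δ, described as the difference between treatment and "control groups is less than the non-inferiority margin (indicating non-inferior bone gain").

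Protocol 8.1 provides that after non-inferiority "a one-side superiority test will be performed at significance level of 5" per cent, but gives no bound for that test. SAP section 1 settles precedence: "The SAP will be used should there be any discrepancies with the protocol".

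**The concern.** With gain positive, μc − μs > −0.5 mm says only that the test arm is less than 0.5 mm worse than control. That is non-inferiority. It is true when the arms are identical, and true when the test arm is somewhat worse. The margin, the prose and the symbols in 5.3 all agree with one another, so a programmer following the SAP would code exactly this test. The protocol cannot repair it, because it states no bound and the SAP takes precedence.

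The trial could therefore report immediate placement as superior on marginal bone when there is no difference, which is the SAP's own planning scenario (expected difference 0 mm in 5.1). Study success under SAP 2.4 rests on non-inferiority alone and is not changed by 5.3. What is at stake is the gated superiority claim, the only other between-arm effectiveness hypothesis planned, since the secondary endpoints are descriptive.

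**Working it through.** **Inputs.** δ = 0.5 mm, SD = 0.5 mm in both arms, expected difference 0, one-sided 5% t-test (SAP 5.1 to 5.3); 46 subjects completed 12 months (SAP 2.1). Assumption: 23 per arm, because the documents give no arm split.

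**1. The plan's sample size reproduces.** Noncentrality is δ / (SD·√(2/n)). At n = 14 it is 0.5 / (0.5 × √(2/14)) = 2.65 with 26 df, giving power 82.4%; n = 13 gives 79.7%. So 14 per arm is right. Then 14 / 0.75 rounds up to 19, and 2 × 19 + 14 = 52, as Protocol 8.1 states.

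**2. Rejection regions at 23 per arm, when the observed pooled SD is 0.5.** The standard error is 0.5 × √(2/23) = 0.1474. The critical t with 44 df is 1.680, and 1.680 × 0.1474 = 0.248.
- 5.2 rejects when the observed difference is below 0.5 − 0.248 = +0.252 mm.
- 5.3 rejects when it is above −0.5 + 0.248 = −0.252 mm.

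Any observed difference between about −0.25 and +0.25 mm passes both and is called superior.

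**3. Claim rates.** For 5.3 alone, the power is that of a noncentral t with noncentrality (d + 0.5) / 0.1474, where d is the true difference. At d = 0 this is 3.39, giving 95.5%. For both tests, write h(s) = 0.5 − 1.680·s·√(2/23), where s is the pooled SD. The rate is Φ((h(s) − d)/0.1474) − Φ((−h(s) − d)/0.1474), averaged over the distribution of s and taken as zero when h(s) ≤ 0. Simulation agrees.

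| True difference (test − control, mm) | 5.3 alone | 5.2 and 5.3 as written |
|---|---|---|
| −0.5 | 5.0% | 5.0% |
| −0.25 | 51.0% | 50.9% |
| −0.2 | 64.0% | 63.9% |
| −0.1 | 84.7% | 83.8% |
| 0 | 95.5% | 91.0% |
| +0.25 | >99.9% | 50.9% |
| +0.5 | >99.9% | 5.0% |

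The 5% level holds at a true difference of −0.5 mm, which is not the boundary of a superiority claim. The last rows show a second effect: as written, the 5.2 gate blocks a test arm that is truly better.

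**4. Range of the as-written claim rate at zero difference.**
- By size, SD 0.5: 65% at 14 per arm, 83% at 19, 94% at 26.
- By split of the 46, SD 0.5: 90.9% for 22/24, about 90.5% for 20/26, 89% for 18/28.
- By SD, 23 per arm: 99% (0.4 mm), 74% (0.6 mm), 34% (0.8 mm). For 5.3 alone: 99.4%, 87.2%, 67.1%.
- Lowest case examined: 14 per arm with SD 0.8, 6%, only because the two tests are rarely passed together (5.3 alone 48.6%).

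With the test arm truly 0.25 mm worse, the rate is 35% at 14 per arm and 55% at 26. At 23 per arm it runs from 21% (SD 0.8) to 67% (SD 0.4).

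**5. The corrected sequence (23 per arm, SD 0.5).** Non-inferiority at −δ, then superiority at 0, claims superiority in 5.0% at d = 0, 0.05% at −0.25 mm, 51% at +0.25 mm and 95.5% at +0.5 mm. Correcting 5.3 alone gives 1.6% at d = 0 but only 6.7% at +0.25 mm, because the gate still points the wrong way. Correcting 5.2 alone makes it identical to 5.3, so every non-inferior result would also be superior.

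**The case against.** The strongest reply is that the direction of the scale is not settled. Section 5 codes gain as positive, but 5.2 and Protocol 8.1 treat a difference of +δ or more as inferior, which fits a loss-positive scale. Protocol 7.3.4 does not decide it: it cites a meta-analysis in which "marginal bone level change for Straumann implants was -0.56 mm", with loss negative, yet its own flagging rule names changes greater than 2.5 mm as an unsigned amount. On a loss-positive scale −δ would be the natural bound for superiority by a margin, with only the inequality reversed.

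The mixture of directions is real, but it does not rescue 5.3. If loss is positive, μc − μs > −δ says that the test arm is not better by 0.5 mm or more, and that is not superiority either. The text is wrong under both codings.

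Two smaller points stand. The 91% depends on SD 0.5 mm and 23 per arm, and it is the error rate for a claim of superiority over zero, a bound that neither document writes down. And this is a gated secondary test: the group summaries would still show the estimated difference, and the study success criterion is untouched. These limit the reach of the error but do not remove it.

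**Conclusion.** The concern holds. Under the SAP's stated coding, 5.3 is a non-inferiority test labelled as superiority, and nothing elsewhere in the documents corrects it. With SD 0.5 mm and 23 per arm (assumed), identical arms would be called superior in 91% of trials under the full sequence and in 95.5% on 5.3 alone, where a superiority claim should carry 5%. At 23 per arm the full-sequence rate runs from 34% to 99% for SDs from 0.8 to 0.4 mm. Passing 5.2 and 5.3 as written shows at most that the difference lies within ±0.5 mm. This must be fixed before any superiority claim is made. The direction of 5.2 has to be settled at the same time, because it is the gate.

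**What to change.** Keep the gain-positive coding of SAP section 5 and amend 5.2 and 5.3 together:
- Non-inferiority (5.2): H0: μc − μs ≤ −δ against H1: μc − μs > −δ.
- Superiority (5.3), only if non-inferiority is shown: H0: μc − μs ≤ 0 against H1: μc − μs > 0, one-sided 5%. This fits the gated test in Protocol 8.1.
- If superiority by a margin is really intended, the bound on this coding is +δ (H1: μc − μs > +δ), and the SAP should say so.

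If the sponsor prefers a loss-positive scale, section 5 must be recoded and the inequality in 5.3 reversed. Either way one coding should run through section 5, 5.2 and 5.3.

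The cost is wording and a line of code, with no new data. Before the primary analysis, SAP 10.6 provides for an amended SAP; after it, the change goes in the clinical study report with its reason. Superiority becomes harder to claim: about 5% at zero difference, 51% at a true +0.25 mm and 95.5% at +0.5 mm (23 per arm, SD 0.5). With the +δ bound the rate at zero difference is below 0.01%.

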6.1 Implant Success and Survival

A surviving implant is defined as the implant being in place at 12 months post-loading. An implant success is defined as a surviving implant that is absent of persistent subjective complaints, recurrent peri-implant infection with suppuration, mobility, and continuous radiolucency around the implant at 12 months post-loading. The implant survival/success at 12 months post-loading will be summarized with the number and percentage of subjects with a surviving/successful implant.

6.2 Buccal Bone Dimensional Change

Buccal bone dimensional change is defined as the buccal bone dimensional thickness at 12 months post-loading minus the dimension thickness at implant loading. The buccal bone dimensional thickness at implant loading and 12 months post-loading will be summarized in addition to the change at 12 months post-loading with the count, mean, standard deviation, median, minimum, and maximum.

6.3 Implant Stability

Implant stability is defined as the ISQ category. The facial-lingual and mesial-distal implant stability at implant placement, implant loading, and final restoration will be summarized with the number and percentage of subjects in each category.

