5.2.4 Implant Stability by Resonance Frequency Analysis (RFA)

An Osstell device is an instrument that uses the RFA method to determine implant stability and osseointegration. The result is presented as an Implant Stability Quotient (ISQ) value of 1 – 100. The higher the ISQ, the more stable the implant. Additional information about the Osstell device can be found at www.osstell.com. Instructions on taking the measurements for this protocol will be provided in the Operation Manual. In general two measurements will be taken from two different angles at implant placement, implant loading, and final restoration.

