8.5 General Statistical Methods

A qualified statistician using validated statistical software will perform all statistical analyses. Unless otherwise specified, the data will be summarized for non-missing subjects in tables listing the mean, standard deviation, minimum, maximum, and number of subjects in a group of continuous data, or number of subjects and percentage in each category for categorical data, as appropriate. In general the denominator for the percentage calculation will be based upon the total number of subjects (N) in the study population for the treatment groups, unless otherwise specified.

All the statistical tests will be based on a 2-sided test at the significance level of 0.05, unless otherwise specified.

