9.1 Implant Stability Quotient (ISQ)

The Implant Stability Quotient (ISQ) is a value from 1-100 indicating the stability of the implant where a higher ISQ means a more stable implant. The ISQ is then categorized as ISQ < 60, ISQ 60 to 69, and ISQ ≥ 70. The ISQ is provided by an Osstell device using the RFA method and both the facial-lingual and mesial-distal implant stability will be obtained.

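### SAP 6.3 reports implant stability only as three ISQ categories, so movement within a category and within a subject goes undescribed; a continuous summary should be added

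*SAP*

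**What the plan says.** Protocol 5.2.4 describes the measurement: "The result is presented as an Implant Stability Quotient (ISQ) value of 1 – 100", where a higher value means a more stable implant. On frequency it says "In general two measurements will be taken from two different angles at implant placement, implant loading, and final restoration". The protocol sets no ISQ cut-points. For continuous data in general, Protocol 8.5 plans that "the data will be summarized for non-missing subjects in tables listing the mean, standard deviation, minimum, maximum" and the number of subjects are tabulated, unless something else is specified.

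The SAP does specify something else. Section 6.3 says "Implant stability is defined as the ISQ category", and that the facial-lingual and mesial-distal readings at the three visits "will be summarized with the number and percentage of subjects in each category". Section 9.1 supplies the bands: "The ISQ is then categorized as ISQ < 60, ISQ 60 to 69, and ISQ ≥ 70". Neither section gives a reason for them. SAP section 1 settles which text governs: "The SAP will be used should there be any discrepancies with the protocol". No secondary endpoint is tested: "All secondary effectiveness endpoints will be summarized descriptively without hypothesis testing" (SAP section 6).

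**The concern.** Once the SAP takes precedence, the protocol's default mean and SD no longer apply to ISQ, and nothing else in the SAP restores a continuous summary. A subject who goes from 61 to 69, or from 71 to 85, is tabulated as unchanged. Because each visit is tabulated separately, the table also cannot show how many subjects rose or fell.

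Implant stability is named in the secondary objectives as an outcome on which the arms are to be compared, and the protocol's rationale says the study should inform how placement timing affects it. In a trial of 53 randomised subjects, a table of three percentages per arm is a thin answer when the underlying score has already been collected.

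**Working it through.** **1. How the SAP treats its effectiveness measures**

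| Measure | SAP section | Continuous summary | Change summarised | Categories |
|---|---|---|---|---|
| Crestal bone level | 5 | yes | yes | yes |
| Buccal bone thickness | 6.2 | yes | yes | no |
| ISQ | 6.3, 9.1 | **no** | **no** | yes |
| Soft tissue margins | 6.4 | yes | yes | no |
| VAS satisfaction | 6.5 | yes | no (no visit before month 12) | no |

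ISQ is the only continuous measure reduced to categories alone. The primary endpoint shows that the SAP already accepts reporting both forms together.

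**2. Size of the loss**

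The documents give no ISQ mean, SD or information figure, so there is no plan figure to reproduce. The sample-size calculation (14 per group) concerns crestal bone level and does not bear on ISQ. What follows rests on assumptions.

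Inputs: the cut-points of SAP 9.1, taken as 59.5 and 69.5 because the bands are in whole numbers; ISQ assumed normal with mean m and SD s; m and s varied over assumed ranges.

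Formula: with z = (cut − m)/s, and a and b the lower and upper z of a band, the share of Fisher information on a mean shift that grouping keeps is the sum over the three bands of [φ(a) − φ(b)]² / [Φ(b) − Φ(a)]. The loss is 1 minus that sum.

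Worked case, m = 70 and s = 8:
- z-values: (59.5 − 70)/8 = −1.3125 and (69.5 − 70)/8 = −0.0625
- φ at these points: 0.1686 and 0.3982
- band probabilities: 0.0947, 0.3804, 0.5249
- terms: 0.1686²/0.0947 = 0.300; (0.1686 − 0.3982)²/0.3804 = 0.139; 0.3982²/0.5249 = 0.302
- kept: 0.74; lost: about 26%

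Loss over a range of assumptions:

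| Mean | SD 6 | SD 7 | SD 8 | SD 10 |
|---|---|---|---|---|
| 65 | 21% | 20% | 19% | 20% |
| 70 | 29% | 27% | 26% | 25% |
| 72 | 37% | 34% | 32% | 29% |
| 75 | 52% | 47% | 43% | 38% |
| 78 | 70% | 63% | 57% | 49% |

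For means 65 to 75 and SDs 6 to 10 the loss is 19% to 52%. It grows once most readings sit in the top band. The smallest loss over means 50 to 89.5 and SDs 3 to 14.75 was 19%.

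**3. What the bands still show, and what they do not**

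- Group level: with SD 8, a rise in mean from 70 to 75 moves the share at 70 or above from about 52% to about 75%. That would be seen in the planned table.
- Subject level, by simulation: with an assumed rise from 72 to 77 (SD 6, correlation 0.5), 69% of subjects stay in the same band, and 33% of all subjects change by 5 points or more without leaving it. The share at 70 or above still goes from 66% to 89%.
- Near the top of the scale: with a rise from 75 to 80 (SD 6, correlation 0.5), 82% stay in the same band and the share at 70 or above goes from 82% to 96%.

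**The case against.** The strongest reply is that this is a matter of presentation. The endpoint is descriptive, and no test, confidence interval or power statement depends on it. A Fisher-information figure measures efficiency for an inference the trial does not plan to make. The raw values are collected and could be tabulated at any time. All of this stands: the percentages above gauge how coarse the bands are and do not describe damage to a planned analysis.

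Second, neither document defines an ISQ change endpoint. Protocol 3.5 and SAP 4.2 list stability as measured at three visits, while the same lists use the word change for buccal bone and soft tissue. That also stands, so change from placement belongs in the table as supplementary description and its absence does not breach the plan.

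A reader might infer four stronger things that the documents do not support:

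- **That change over time is hidden.** Percentages at three visits still show group movement across 60 and 70. Only movement inside a band and within subjects is lost.
- **That a fixed share of information is known to be discarded.** No ISQ distribution is given, and the result moves widely with the assumed mean and SD.
- **That the relevant sample is 46, or 23 per arm.** SAP 2.1 gives 46 as the number who completed month 12. The last ISQ visit is final restoration, about 10 weeks after loading. The ISQ denominators, and the split of completers by arm, are not stated.
- **That the bands were chosen after looking at the data.** They appear in a SAP written after 46 subjects had passed their ISQ visits in an unblinded study, and carry no rationale. Nothing shows that the choice was data-driven. Reporting the raw score would make the question moot.

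**Conclusion.** The point holds as a minor, nearly free improvement. SAP 6.3 makes three-band counts the sole summary of a continuous secondary measure. This departs from the protocol's default and from the SAP's own treatment of every comparable measure. The consequence is a less informative description of stability by arm, with within-band movement and within-subject change left out.

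The 19% to 52% range is conditional on normality, the assumed means (65 to 75) and the assumed SDs (6 to 10). It would be higher if most readings lie well above 70, for example 70% at mean 78 and SD 6. The primary endpoint, its test and the success criterion are unaffected.

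**What to change.** In SAP 6.3, define implant stability as the ISQ value. For each arm, direction (facial-lingual, mesial-distal) and visit (placement, loading, final restoration), report count, mean, SD, median, minimum and maximum. Add the same statistics for change from placement to loading and from placement to final restoration, labelled as supplementary description. Keep the three bands of SAP 9.1 as an additional row, and show the number of subjects with a reading at each visit so that the denominators are explicit.

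The cost is one SAP sentence and one table, with no new data. SAP 10.6 already provides the route: an amended SAP if the primary endpoint has not yet been analysed, otherwise a documented change in the clinical study report.
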